11.5.2. Handling of Missing Data

Element	Reporting Detail
General	
 Missing data occurs when any requested data is not provided, leading to blank fields on the collection instrument: 
 These data will be indicated by the use of a "blank" in participant listing displays. Unless all data for a specific visit are missing in which case the data is excluded from the table. Answers such as "Not applicable" and "Not evaluable" are not considered to be missing data and should be displayed as such.
Outliers	
 Any participants excluded from the summaries and/or statistical analyses will be documented along with the reason for exclusion in the clinical study report.

11.5.2.1. Handling of Missing and Partial Dates

Element	Reporting Detail
General	
 Partial dates will be displayed as captured in participant listing displays.
Adverse Events	
 The eCRF allows for the possibility of partial dates (i.e., only month and year) to be recorded for AE start and end dates; that is, the day of the month may be missing. In such a case, the following conventions will be applied for calculating the time to onset and the duration of the event: 
 Missing Start Day: First of the month will be used unless this is before the start date of study treatment; in this case the study treatment start date will be used and hence the event is considered On-treatment as per Appendix 2: Study Phases and Treatment Emergent Adverse Events. Missing Stop Day: Last day of the month will be used, unless this is after the stop date of study treatment; in this case the study treatment stop date will be used. Completely missing start or end dates will remain missing, with no imputation applied. Consequently, time to onset and duration of such events will be missing.
Concomitant Medications/Medical History	
 Partial dates for any concomitant medications recorded in the eCRF will be imputed using the following convention: 
 If the partial date is a start date, a '01' will be used for the day and 'Jan' will be used for the month If the partial date is a stop date, a '28/29/30/31' will be used for the day (dependent on the month and year) and 'Dec' will be used for the month. The recorded partial date will be displayed in listings.

11.6. Appendix 6: Division of AIDS (DAIDS) Table for Grading the Severity of Adult and Pediatric Adverse Events

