8.1. Adverse Events Analyses

Adverse events (AEs) analyses including the analysis of AEs, serious (SAEs), and other significant AEs will be based on VH/GSK's Integrated Data Standards Library standards. The details of the planned displays are provided in Appendix 9: List of Data Displays.

Adverse events will be assigned to the last treatment received prior to start date/time of the AE. If no time was reported for an AE and the date is the same as date of dosing, the AE will be assigned to the treatment dosed on that day. Adverse events occurring after the last dose date and time + 5 days (Day 6 and beyond for each treatment period) and before the dose date and time of the next treatment will not be summarized but will be listed.

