11.2.2. Treatment Emergent Flag for Adverse Events

Flag	Definition
Treatment Emergent	
 • If AE onset date and time is on or after treatment start date and time & on or before treatment stop date and time + 5 days within each treatment period. • Study Treatment Start Date and Time \leq AE Start Date and Time \leq Study Treatment Stop Date and Time + 5 days within each treatment period. • If the AE onset date is completely missing, the AE is considered as treatment emergent.

NOTES:

- If the study treatment stop date is missing, then the AE will be considered to be On-Treatment.
- Please refer to Appendix 5: Reporting Standards for Missing Data for handling of missing and partial dates for AEs. Use the rules in this table if the AE onset date is completely missing.

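### The SAP caps a missing AE stop day at a dosing day, which can put the stop before onset; on one reading its start-day rule also counts events under an earlier treatment

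*SAP*

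**What the plan says.** SAP 11.5.2.1 expects some AE dates to lack the day of the month and gives two rules.

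- **Missing stop day.** The default is month-end. Where month-end comes later than the end of treatment, the SAP overrides it: "in this case the study treatment stop date will be used".
- **Missing start day.** The default is the 1st. Where the 1st comes earlier than the beginning of treatment, the SAP overrides it too: "in this case the study treatment start date will be used and hence the event is considered On-treatment".

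The section does not say whether the treatment start and stop dates are those of the whole study or of one period. It has no condition that a stop date must not precede onset. It gives the purpose as follows: "the following conventions will be applied for calculating the time to onset and the duration of the event".

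Two other sections depend on AE dates. SAP 11.2.2 defines treatment-emergent events as those from dosing to treatment stop + 5 days within each period, and its notes say: "Please refer to Appendix 5: Reporting Standards for Missing Data for handling of missing and partial dates for AEs". SAP 8.1 sets the treatment: "Adverse events will be assigned to the last treatment received prior to start date/time of the AE". It adds a rule for a missing time on a dosing day, but none for a missing day.

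The Protocol synopsis gives one dose per period, on Day 1. Participants stay in the clinic until Day 5 of the last period.

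**The concern.** These rules suit continuous dosing, where the treatment stop date lies near the end of observation and there is one treatment to assign. Neither holds here. With a single dose per period, every treatment stop date is a dosing day, while AEs are still being collected and are treatment-emergent for 5 more days. The stop cap leaves out that + 5 days, so it cuts events off inside the SAP's own on-treatment window.

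For start days, a month can contain two or three doses of different treatments. The first of the month, or the first dose, is then a poor guide to the treatment that preceded the event.

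At stake are AE durations that cannot be true and AE counts by formulation (Part 1) or meal condition (Part 2), which serve the secondary safety objective. With about 18 participants per part, one participant is 1/18 = 5.6% of a treatment column, so one moved event shows.

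**Working it through.** **Inputs.** Doses are at least 7 days apart, less a 4-hour allowance (SAP 2.3), taken here as Days 1, 8 and 15 in Part 1 and Days 1 and 8 in Part 2. Discharge is then Day 19 or Day 12. The Protocol's study durations agree: 35 + 2 + 19 = 56 days and 35 + 2 + 12 = 49 days. The plan gives no figure of its own to reproduce on this point.

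**Missing stop day.** Imputed stop = the earlier of month-end and the treatment stop date. If onset is later than the treatment stop date, the imputed stop always precedes onset, whatever the true duration or calendar month. So it is enough to count onset days, taken as equally likely.

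| Meaning of stop date | Part 1 | Part 2 |
|---|---|---|
| Last dose in the study | Days 2–5 of Period 3: 4/19 = 21% | Days 2–5 of Period 2: 4/12 = 33% |
| Dose of that period | (6 + 6 + 4)/19 = 84% | (6 + 4)/12 = 83% |

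Under the first meaning, events starting in earlier periods are not affected. Example: doses on 1, 8 and 15 June, onset 16 June, stop recorded as June with no day. Month-end is after 15 June, so the imputed stop is 15 June, one day before onset.

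**Missing start day.** Assume that the start date means the Period 1 dose and that the imputed date feeds SAP 8.1. Imputed start = the later of the first of the month and the Period 1 dose. Take true onset on Days 1–5 of a period, equally likely, and every Period 1 date in a 365-day year.

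- A Period 2 or Period 3 event stays in its own period only if the first of a month falls between that period's dose and onset. That span is 1 to 5 days, mean 3, so the chance is 12 × 3/365 = 9.9%. About 90% are misassigned.
- A Period 3 event avoids Period 1 only if the first of a month falls between the Period 2 dose and onset. The mean span is 7 + 3 = 10 days, so the chance is 12 × 10/365 = 32.9%. About 67% land in Period 1. For Period 2 events the figure is 90%.
- Over all periods: (0 + 90 + 90)/3 = 60% in Part 1 and (0 + 90)/2 = 45% in Part 2.
- Some leave the summaries. If the imputed start is Day 7 of an earlier period, it is beyond dose + 5 days and SAP 8.1 lists it only: 12/365 = 3% of Period 2 events and 24/365 = 7% of Period 3 events.

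Examples, each with the onset recorded as June and no day:

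| Doses | True onset | Imputed start | Result |
|---|---|---|---|
| 1, 8, 15 June | 16 June (Period 3) | 1 June | Counted under Period 1 |
| 25 May, 1 June, 8 June | 9 June (Period 3) | 1 June | Counted under Period 2 |
| 26 May, 2 June, 9 June | 10 June (Period 3) | 1 June, Period 1 Day 7 | Listed only |

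The last row sits oddly beside SAP 11.2.2, where a completely missing onset date counts as treatment-emergent. Knowing the month can remove an event that would be kept if nothing were known.

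**The case against.** The strongest case against has four parts.

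1. **Start date by period.** SAP 11.2.2 applies treatment start and stop within each period. Read that way, the imputed start is never before that period's dose nor after true onset, so no event is misassigned. This is right if the period is known. But a date without a day does not supply the period, and the documents show no eCRF field that records it.
2. **Stated purpose.** SAP 11.5.2.1 names time to onset and duration, and SAP 8.1 does not mention imputed dates. No AE table title in SAP 11.9.5 concerns duration. So the effect on treatment counts is an inference. It is a reasonable one: the start rule itself classes the event as on-treatment, SAP 11.2.2 points to it, and SAP 8.1 offers nothing else for a partial date.
3. **Rarity.** Participants are confined from Day -2 to final discharge, so onset days should nearly always be known. The likeliest partial date is a stop after discharge, when onset and treatment are already recorded. This stands.
4. **Use.** Safety is summarised descriptively with no formal analysis (Protocol 9.4.2), and Part 2's safety objective states no explicit comparison. This also stands, and limits the weight.

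None of this answers the stop-day rule. It gives impossible dates on either meaning of the stop date, and the per-period meaning makes it worse.

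**Conclusion.** The stop-day defect is certain from the text: a stated rule gives stop dates before onset. Its size is 21% (Part 1) and 33% (Part 2) of onset days if the stop date is the last dose, or 84% and 83% if it is the dose of that period. These are conditional on a missing stop day and assume equally likely onset days and exact 7-day spacing.

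The start-day problem is conditional. It needs the whole-study meaning of start date and the use of the imputed date in SAP 8.1. Then about 60% (Part 1) and 45% (Part 2) of events with a missing start day and true onset on Days 1–5 are counted under an earlier treatment, usually Period 1's.

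A reader might infer that every AE with a partial date goes to the wrong treatment or gets a negative duration. The documents do not support that. Many such events are handled correctly, a missing stop day cannot alter treatment because SAP 8.1 uses the start, and Period 1 is the usual landing place but not the only one. Nor can the 84%/83% be combined with the 60%/45%: they rest on different readings and are not joint effects.

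Practical weight is low. Partial dates should be rare, listings show dates as captured, and the primary PK analysis is untouched. The correction is cheap and should be made before unblinding.

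**What to change.** Amend SAP 11.5.2.1 and add a matching sentence to SAP 8.1.

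1. **Missing stop day.** Drop the cap at the treatment stop date. Use the last day of the recorded month, or the last study contact if that falls in the same month, and never a date before onset. The same-month condition keeps a stop recorded in a month after discharge from being moved into the wrong month. The onset condition makes negative durations impossible by construction.
2. **Missing start day.** Do not let the imputed day decide treatment. Define the start date by period. If the eCRF records the AE's period, use it. If not, narrow the candidate periods by the recorded month and the known stop date. Count events that are still ambiguous by one pre-stated, flagged rule, for example under each candidate treatment.

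The cost is a few SAP sentences and minor programming. A few events may stay ambiguous, because no imputed day can recover the period when the month contains several doses.

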11.6.1. Laboratory Values

The Division of AIDS (DAIDS) grading for severity of laboratory toxicities and clinical AEs, version 2.1, July 2017 (2) will be used to assign grades to laboratory values.

Laboratory results are converted to use SI units; only the numeric part of the criteria will be used. If for a laboratory parameter there are multiple grades sharing the same criteria, the maximum grade will be used. The table below outlines the planned laboratory assessments to be done in the study.

Laboratory Assessments	Parameters		
Hematology	Platelet Count	RBC Indices: Mean corpuscular volume Mean corpuscular hemoglobin	WBC count with Differential: Neutrophils Lymphocytes Monocytes Eosinophils Basophils Absolute neutrophil count
	RBC Count		
	Hemoglobin		
	Hematocrit		
Clinical Chemistry	BUN Glucose (fasting) Creatinine Potassium Sodium Calcium Chloride Phosphorus	Carbon dioxide Aspartate Aminotransferase Alanine Aminotransferase Gamma-glutamyl transferase Total and direct bilirubin Lactate dehydrogenase Total cholesterol Triglycerides Alkaline phosphatase ²	Total Protein Albumin Globulin Anion gap Uric acid Creatine phosphokinase Serum lipase Serum amylase
Routine Urinalysis	
 Specific gravity pH, glucose, protein, blood, ketones, bilirubin, urobilinogen, nitrite, leukocyte esterase by dipstick Microscopic examination (if blood, leukocyte esterase, or protein is abnormal) 		
Pregnancy testing	
 Highly sensitive human chorionic gonadotropin (hCG) pregnancy test (as needed for women of childbearing potential)³ 		
Other Screening Tests	
 Molecular test for SARS-CoV-2 (Two consecutive approved molecular tests [polymerase chain reaction or antigen test]. The first test should be performed ≥ 7 days prior to admission and the second test will be performed on Day -2 after admission to the clinic. Follicle-stimulating hormone (as needed in women of non-childbearing potential only) Serology: HIV-1 and -2 antigen/antibody immunoassay, hepatitis B surface antigen, hepatitis C antibody Alcohol, cotinine, and drug screen (to include at minimum amphetamines, barbiturates, cannabinoids, cocaine, or phencyclidine, or nonprescribed opiates, oxycodone, benzodiazepines, methadone, or tricyclic antidepressants) 		

1. Details of liver chemistry stopping criteria and required actions and follow-up assessments after liver stopping or monitoring event are given in Section 7.1 and Appendix 5. All events of ALT $\geq 3 \times$ ULN and bilirubin $\geq 2 \times$ ULN ($>35\%$ direct bilirubin) or ALT $\geq 3 \times$ ULN and INR > 1.5 , if INR measured, which may indicate severe liver injury (possible Hy's Law), must be reported as an SAE (excluding studies of hepatic impairment or cirrhosis).
2. If alkaline phosphatase is elevated, consider fractionating.
3. Local urine pregnancy testing will be standard for the protocol unless serum testing is required by local regulation or IRB/IEC.

11.7. Appendix 7: Values of Potential Clinical Importance

11.7.1. ECG

ECG Parameter	Units	Potential Clinically Important Range	
		Lower	Upper
Absolute			
Absolute QTc Interval	msec	< 320	> 450*
Absolute PR Interval	msec	< 110	> 220
Absolute QRS Interval	msec	< 75	> 110
Change from Baseline			
Increase from Baseline QTc	msec		> 60

* Exclusion criteria: Confirmed QTcF value >450 msec at screening or Day 1.

11.7.2. Vital Signs

Vital Sign Parameter (Absolute)	Units	Potential Clinically Important Range	
		Lower	Upper
Systolic Blood Pressure	mmHg	< 85	> 160
Diastolic Blood Pressure	mmHg	< 45	> 100
Heart Rate	bpm	< 40	> 110

11.8. Appendix 8: Abbreviations & Trademarks

11.8.1. Abbreviations

Abbreviation	Description
AE	Adverse Event
ANOVA	Analysis of Variance
AUC	Area under the plasma concentration-time curve
AUC($0-\infty$)	AUC from time 0 extrapolated to infinity
AUC(0-t)	AUC from Time 0 to Time t
BA	Bioavailability
BMI	Body Mass Index
bpm	Beats per minute
CDISC	Clinical Data Interchange Standards Consortium
CI	Confidence interval
CL/F	Apparent oral clearance
Cmax	Maximum observed concentration
COVID-19	Coronavirus disease
CRF	Case report form
CSR	Clinical Study Report
C-SSRS	Columbia-Suicide Severity Rating Scale
CV	Coefficient of variation
CVb	Coefficient of variation (Between)
DAIDS	Division of AIDS
DBF	Database Freeze
DBR	Database Release
DP	Decimal Places
ECG	Electrocardiogram
FDA	Food and Drug Administration
GSK	GlaxoSmithKline
hCG	Human Chorionic Gonadotropin
HIV	Human Immunodeficiency Virus
ICH	International Council On Harmonisation
IDSL	Integrated Data Standards Library
IRB	Institutional Review Board
LLN	Lower Limit of Normal
MedDRA	Medical Dictionary for Regulatory Activities
PI	Principal Investigator
PK	Pharmacokinetic
PT	Preferred Term
QTcF	QTc using the Fridericia formula
RAP	Reporting & Analysis Plan
SAC	Statistical Analysis Complete
SAE	Serious Adverse Event
SARS-CoV2	Severe Acute Respiratory Syndrome Coronavirus 2
SD	Standard Deviation
SDTM	Study Data Tabulation Model
SMQ	Standardized MedDRA Query
SOC	System Organ Class
t _{1/2}	Apparent Terminal Phase Half-life

Abbreviation	Description
Tmax	Time of Maximum Observed Concentration
TLF	Tables, listings, figures
ULN	Upper Limit of Normal
VH	ViiV Healthcare

11.8.2. Trademarks

Trademarks of ViiV Healthcare	Trademarks not owned by ViiV Healthcare
Tivicay	DAIDS SAS WinNonlin

11.9. Appendix 9: List of Data Displays

11.9.1. Data Display Numbering

The following numbering will be applied for RAP generated displays:

Section	Tables	Figures
Study Population	1.1 to 1.14	
Safety	2.1 to 2.56	2.1 to 2.2
Pharmacokinetic	3.1 to 3.14	3.1 to 3.18
Section	Listings	
ICH Listings	1 to 72	
Other Listings	73 to 80	

11.9.2. Mock Example Shell Referencing

Non-IDSL specifications will be referenced as indicated and if required example mock-up displays provided in the Table/Listing/Figure Shells.

Section	Figure	Table	Listing
Study Population	POP_Fn	POP_Tn	POP_Ln
Safety	SAFE_Fn	SAFE_Tn	SAFE_Ln
Pharmacokinetic	PK_Fn	PK_Tn	PK_Ln

NOTES:

- Non-Standard displays are indicated in the 'IDSL / Example Shell' or 'Programming Notes' column as '[Non-Standard] + Reference.'

11.9.3. Deliverables

Delivery	Description
SAC	Final Statistical Analysis Complete

11.9.4. Study Population Tables

Study Population Tables					
No.	Population	IDSL / Example Shell	Title	Programming Notes	Deliverable [Priority]
Subject Disposition					
1.1.	Enrolled	NS1	Summary of Number of Subjects Enrolled		SAC
1.2.	Safety	ES1	Summary of Subject Disposition for the Subject Conclusion Record – Part 1		SAC
1.3.	Safety	ES1	Summary of Subject Disposition for the Subject Conclusion Record – Part 2		SAC
1.4.	Screened	SD1	Summary of Screening Status and Reasons for Screen Failures		SAC
1.5.	Randomized	SP1	Summary of Study Populations – Part 1		SAC
1.6.	Randomized	SP1	Summary of Study Populations – Part 2		SAC
Protocol Deviations					
1.7.	Safety	DV1	Summary of Important Protocol Deviations – Part 1		SAC
1.8.	Safety	DV1	Summary of Important Protocol Deviations – Part 2		SAC
Demographic and Baseline Characteristics					
1.9.	Safety	DM1	Summary of Demographic Characteristics – Part 1		SAC
1.10.	Safety	DM1	Summary of Demographic Characteristics – Part 2		SAC
1.11.	Safety	DM5	Summary of Race and Racial Combinations – Part 1		SAC
1.12.	Safety	DM5	Summary of Race and Racial Combinations – Part 2		SAC
1.13.	Safety	DM11	Summary of Age Ranges – Part 1		SAC

Study Population Tables					
No.	Population	IDSL / Example Shell	Title	Programming Notes	Deliverable [Priority]
1.14.	Safety	DM11	Summary of Age Ranges – Part 2		SAC

11.9.5. Safety Tables

Safety: Tables					
No.	Population	IDSL / Example Shell	Title	Programming Notes	Deliverable [Priority]
Adverse Events (AEs)					
2.1.	Safety	AE1xo	Summary of Adverse Events by System Organ Class and Preferred Term – Part 1		SAC
2.2.	Safety	AE1xo	Summary of Adverse Events by System Organ Class and Preferred Term – Part 2		SAC
2.3.	Safety	AE1xo	Summary of Drug-Related Adverse Events by System Organ Class and Preferred Term – Part 1		SAC
2.4.	Safety	AE1xo	Summary of Drug-Related Adverse Events by System Organ Class and Preferred Term – Part 2		SAC
2.5.	Safety	AE3	Summary of Common (>=5%) Adverse Events by Overall Frequency – Part 1		SAC
2.6.	Safety	AE3	Summary of Common (>=5%) Adverse Events by Overall Frequency – Part 2		SAC
2.7.	Safety	AE15	Summary of Common (>=5%) Non-serious Adverse Events by System Organ Class and Preferred Term – Part 1 (Number of Subjects and Occurrences)		SAC

Safety: Tables					
No.	Population	IDSL / Example Shell	Title	Programming Notes	Deliverable [Priority]
2.8.	Safety	AE15	Summary of Common (>=5%) Non-serious Adverse Events by System Organ Class and Preferred Term – Part 2 (Number of Subjects and Occurrences)		SAC
2.9.	Safety	AE16	Summary of Serious Adverse Events by System Organ Class and Preferred Term – Part 1 (Number of Subjects and Occurrences)		SAC
2.10.	Safety	AE16	Summary of Serious Adverse Events by System Organ Class and Preferred Term – Part 2 (Number of Subjects and Occurrences)		SAC
2.11.	Safety	AE5A	Summary of Adverse Events by System Organ Class and Preferred Term and Maximum Intensity – Part 1		SAC
2.12.	Safety	AE5A	Summary of Adverse Events by System Organ Class and Preferred Term and Maximum Intensity – Part 2		SAC
2.13.	Safety	AE1xo	Summary of Adverse Events of Special Interest by System Organ Class and Preferred Term – Part 1		SAC
2.14.	Safety	AE1xo	Summary of Adverse Events of Special Interest by System Organ Class and Preferred Term – Part 2		SAC
Laboratory: Chemistry					
2.15.	Safety	LB1	Summary of Clinical Chemistry Data – Part 1		SAC
2.16.	Safety	LB1	Summary of Clinical Chemistry Data – Part 2		SAC
2.17.	Safety	LB1	Summary of Clinical Chemistry Changes from Baseline – Part 1		SAC
2.18.	Safety	LB1	Summary of Clinical Chemistry Changes from Baseline – Part 2		SAC
2.19.	Safety	LB16	Summary of Clinical Chemistry Results by Maximum Grade Increase Post-Baseline Relative to Baseline – Part 1		SAC

Safety: Tables					
No.	Population	IDSL / Example Shell	Title	Programming Notes	Deliverable [Priority]
2.20.	Safety	LB16	Summary of Clinical Chemistry Results by Maximum Grade Increase Post-Baseline Relative to Baseline – Part 2		SAC
Laboratory: Hematology					
2.21.	Safety	LB1	Summary of Hematology Data – Part 1		SAC
2.22.	Safety	LB1	Summary of Hematology Data – Part 2		SAC
2.23.	Safety	LB1	Summary of Hematology Changes from Baseline – Part 1		SAC
2.24.	Safety	LB1	Summary of Hematology Changes from Baseline – Part 2		SAC
2.25.	Safety	LB16	Summary of Hematology Results by Maximum Grade Increase Post-Baseline Relative to Baseline – Part 1		SAC
2.26.	Safety	LB16	Summary of Hematology Results by Maximum Grade Increase Post-Baseline Relative to Baseline – Part 2		SAC
Laboratory: Urinalysis					
2.27.	Safety	LB1	Summary of Urine Concentration – Part 1		SAC
2.28.	Safety	LB1	Summary of Urine Concentration – Part 2		SAC
2.29.	Safety	LB1	Summary of Urine Concentration Changes from Baseline – Part 1		SAC
2.30.	Safety	LB1	Summary of Urine Concentration Changes from Baseline – Part 2		SAC
2.31.	Safety	UR3	Summary of Urinalysis Dipstick Results – Part 1		SAC
2.32.	Safety	UR3	Summary of Urinalysis Dipstick Results – Part 2		SAC
2.33.	Safety	LB16	Summary of Urinalysis by Maximum Grade Increase Post-Baseline Relative to Baseline – Part 1		SAC
2.34.	Safety	LB16	Summary of Urinalysis by Maximum Grade Increase Post-Baseline Relative to Baseline – Part 2		SAC

Safety: Tables					
No.	Population	IDSL / Example Shell	Title	Programming Notes	Deliverable [Priority]
ECG					
2.35.	Safety	SAFE_T1	Summary of ECG Findings – Part 1		SAC
2.36.	Safety	SAFE_T1	Summary of ECG Findings – Part 2		SAC
2.37.	Safety	EG2	Summary of ECG Values – Part 1		SAC
2.38.	Safety	EG2	Summary of ECG Values – Part 2		SAC
2.39.	Safety	EG2	Summary of ECG Changes from Baseline – Part 1		SAC
2.40.	Safety	EG2	Summary of ECG Changes from Baseline – Part 2		SAC
2.41.	Safety	EG10	Summary of Maximum QTc Values Post-Baseline Relative to Baseline by Category – Part 1		SAC
2.42.	Safety	EG10	Summary of Maximum QTc Values Post-Baseline Relative to Baseline by Category – Part 2		SAC
2.43.	Safety	EG11	Summary of Maximum Increase in QTc Values Post-Baseline Relative to Baseline by Category – Part 1		SAC
2.44.	Safety	EG11	Summary of Maximum Increase in QTc Values Post-Baseline Relative to Baseline by Category – Part 2		SAC
Vital Signs					
2.45.	Safety	VS1	Summary of Vital Signs – Part 1		SAC
2.46.	Safety	VS1	Summary of Vital Signs – Part 2		SAC
2.47.	Safety	VS1	Summary of Vital Sign Changes from Baseline – Part 1		SAC
2.48.	Safety	VS1	Summary of Vital Sign Changes from Baseline – Part 2		SAC
C-SSRS					

Safety: Tables					
No.	Population	IDSL / Example Shell	Title	Programming Notes	Deliverable [Priority]
2.49	Safety	CSSRS4	Listing of C-SSRS Suicidal Ideation and Behavior Data – Part 1		SAC
2.50	Safety	CSSRS4	Listing of C-SSRS Suicidal Ideation and Behavior Data – Part 2		SAC
SARS-CoV-2					
2.51	Safety	PAN1	Summary of COVID-19 Assessments – Part 1		SAC
2.52	Safety	PAN1	Summary of COVID-19 Assessments – Part 2		SAC
2.53	Safety	SAFE_T2	Summary of COVID-19 Adverse Event Summary – Part 1		SAC
2.54	Safety	SAFE_T2	Summary of COVID-19 Adverse Event Summary – Part 2		SAC
2.55	Safety	PAN3	Summary of COVID-19 Symptoms for Subjects with Adverse Event – Part 1		SAC
2.56	Safety	PAN3	Summary of COVID-19 Symptoms for Subjects with Adverse Event – Part 2		SAC

